### **14.1 Data Sets Analyzed**

All eligible participants who are randomized into the study and receive at least one dose of the study drug (the Safety Population) will be included in the safety analysis.

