### 2.1 Risk / Benefit Assessment

**Risk:** Inhaled n-acetylcysteine (NAC) is approved for the treatment of mucus associated airway disease, including asthma. The main side effect from inhaled n-acetylcysteine (NAC) is bronchospasm. We find that co-administering NAC and albuterol effectively prevents excessive bronchoconstriction in asthmatic patients. Specifically, in eight asthmatics that were given doses of 20% NAC as high as 3 mL together with 3 mL of albuterol, the largest FEV1 decline was 6%.

**Benefit:** Mucus plugs cause airway obstruction and symptoms of dyspnea. The role of mucolytics in decreasing plugs and increasing FEV1 has not been well studied. Our preliminary data, utilizing CT imaging and a novel scoring system, can identify and target a

subgroup of patients who may benefit from inhaled mucolytic treatment more so than the asthmatic population as a whole.

To minimize risk, study participants will be administered the first two treatments under the supervision of the study team in the Airway Clinical Research Center and will only be eligible to remain in the study if their post-treatment FEV1s are greater than 80% of their pre-treatment, pre-bronchodilator FEV1.

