### 6.2 Inclusion Criteria

1. Male or female between the ages of 18 and 80 years of age at Visit 1

2. Written informed consent obtained from subject and ability for subject to comply with the requirements of the study.
3. Able to perform reproducible spirometry according to ATS criteria
4. Physiological evidence of airflow obstruction (FEV1 bronchodilator reversibility of  $\geq 12\%$  or hyperreactivity to methacholine reflected by a methacholine PC20  $\leq 16$  mg/mL) Historical methacholine data may be allowed. An exception will be made for enrollees whose FEV1 is  $< 50\%$  predicted (precluding methacholine challenge testing. If bronchodilator reversibility is  $< 12\%$  in these participants, a diagnosis of asthma acceptable to the investigator is sufficient for inclusion in ENACT.
4. Clinical history of asthma per patient report or medical record
5. Pre-bronchodilator FEV1  $> 35\%$  predicted
6. Post-bronchodilator FEV1  $> 40\%$  but  $< 90\%$  predicted. If the participant has past evidence of mucus impaction as described by a radiologist on a prior chest CT scan, then post-bronchodilator FEV1 needs to be  $> 40\%$  but  $< 95\%$  predicted.
7. Asthma requiring treatment with inhaled corticosteroids (ICS) for 3 months or greater.
8. CT mucus score  $\geq 5$
9. Ability to tolerate study drug reflected by a post-treatment FEV1  $\geq 80\%$  of pre-treatment, pre-bronchodilator FEV1

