#### **9.5 Visit 4 (Day 7)**

1. Review and record changes to concomitant medications.
2. Perform and record vital signs.
3. Perform and record oximetry.
4. Perform and record urine pregnancy test
5. Perform and record fractional exhaled nitric oxide (FeNO) measurement.
6. Perform and record spirometry.
7. Perform and record post-bronchodilator reversibility.
8. Perform and record plethysmography with bronchodilation.
9. Randomize
10. Provide education on use of personal nebulizer and administration of study medication.
11. Administer first two treatments of study drug treatment, spaced 4-6 hours. FEV1 measurements should be taken before and after each treatment.
12. Dispense study drug and initiate study diary if subject's post-treatment FEV1 is greater than 80% of pre-treatment FEV1.
13. Schedule participant for phone follow-up in 3-5 days and visit 5 in 7 days.

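### Section 14.1 limits the Safety Population to eligible participants, but one eligibility criterion is a drug-tolerance check made after randomisation and dosing, so first-period failures can be read as excluded

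*Combined protocol and SAP*

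**What the plan says.** Section 14.1 is the only place where an analysis set is defined. It covers "All eligible participants who are randomized into the study and receive at least one dose of the study drug (the Safety Population". Being eligible stands there as a condition in addition to being randomised and dosed.

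Section 6.1 makes eligibility a matter of meeting the inclusion and exclusion criteria. The last inclusion criterion in 6.2, which is number 10 in the synopsis, begins "Ability to tolerate study drug reflected by a post-treatment FEV1" and requires that value to be at least 80% of the pre-treatment, pre-bronchodilator FEV1.

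Section 9.5 (Visit 4) fixes the order. Step 9 is randomisation. Step 11 is "Administer first two treatments of study drug treatment, spaced 4-6 hours. FEV1 measurements should be taken before and after each treatment". Step 12 is "Dispense study drug and initiate study diary if subject's post-treatment FEV1 is greater than 80% of pre-treatment FEV1". Section 9.10 (Visit 8) repeats the dosing and the check at the start of period 2.

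Section 2.1 says participants "will only be eligible to remain in the study if their post-treatment FEV1s are greater than 80% of their pre-treatment, pre-bronchodilator FEV1", and also states: "The main side effect from inhaled n-acetylcysteine (NAC) is bronchospasm".

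**The concern.** A safety set should contain everyone exposed, whatever happened to them after exposure. Here one condition for entering the set can be failed because of a reaction to the blinded treatment. The reaction in question, a marked fall in FEV1 after inhalation, is the more severe form of the harm the protocol itself expects from NAC.

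The effect is also uneven between sequences. A participant given NAC first who reacts at Visit 4 fails an inclusion criterion. A participant given placebo first will usually have met that criterion on saline before receiving NAC at Visit 8. Section 11.3 replaces participants who withdraw, so a loss at Visit 4 might not show in the final count. Incidence of adverse events is the only safety evaluation in the synopsis, and with 36 participants one or two such events are a material part of the safety result.

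**Working it through.** The plan states no figure on this point, so the check is mainly one of wording, followed by an illustration of size.

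**Wording**

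1. Membership under 14.1 requires eligible, randomised and dosed.
2. Eligible means meeting the inclusion criteria (6.1).
3. Tolerating study drug is an inclusion criterion (6.2, synopsis).
4. It can be assessed only at step 12 of Visit 4, after randomisation (step 9) and dosing (step 11).
5. A Visit 4 failure is therefore randomised and dosed but, taken literally, not eligible, and so is outside the set. On this reading the count of Visit 4 failures in the safety tables is zero by construction.
6. The same does not follow for Visit 8. A participant who passed at Visit 4 has met the criterion. A Visit 8 failure is lost only if the second check is also read as part of eligibility.

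**Size**

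Inputs: 36 participants randomised 1:1 (7.1), so 36 / 2 = 18 NAC-first. The documents give no rate of failing the check on NAC, so 5–15% is an assumption.

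- Expected NAC-first failures at Visit 4: 0.05 × 18 = 0.9 and 0.15 × 18 = 2.7, that is, about 1 to 3.
- Chance of at least one: 1 − 0.95^18 = 0.60 and 1 − 0.85^18 = 0.95.

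The only tolerance data are in 2.1: eight people with asthma, largest FEV1 decline 6%, so 0 of 8 had a fall of 20% or more. The exact one-sided 95% upper limit for 0 of 8 is 1 − 0.05^(1/8) = 0.312, or 31%. For a two-sided 95% interval it is 1 − 0.025^(1/8) = 0.369, or 37%. Eight participants therefore cannot exclude a rate of 5–15%. The comparison is also indirect: the pilot used 20% NAC at up to 3 mL with 3 mL of albuterol, and the trial uses 3 mL of 10% NAC with 0.5 mL of albuterol.

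**Consistency of the check itself**

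- Synopsis and 6.2: at least 80% of the pre-treatment, pre-bronchodilator FEV1.
- Section 2.1: greater than 80% of that same baseline.
- Sections 9.5 and 9.10: greater than 80% of the pre-treatment FEV1, without saying whether before or after bronchodilator. At both visits bronchodilator testing comes before dosing.

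These give different answers at exactly 80%, and may give different answers elsewhere if the baseline differs.

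**The case against.** The strongest reply is that *eligible* in 14.1 means eligible before randomisation. Section 4.1 says eligibility is determined from screening data. Section 7.1 speaks of eligible patients being randomly assigned, which puts eligibility first, and 14.1 uses the same order. If passing the check were required, everyone in the set would already have been dosed, and the condition of at least one dose would add nothing. Section 2.1 speaks of being eligible to remain in the study, which describes continuation rather than entry.

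This reading is reasonable and may be what was intended. It does not settle the matter, because 6.1 and 6.2 still place the tolerance check inside eligibility and no passage says that participants who fail it stay in the safety analysis. On this reading too the word is unhelpful: it would drop anyone randomised in breach of a screening criterion, which section 12 foresees as a protocol violation, although that person was also exposed.

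It is also fair to say that data would not be lost. Adverse events are captured throughout (8.1.17), asked about at each visit (10.1) and recorded at the early withdrawal visit (9.14). Serious events are collected from consent (10.2.1), and section 13 provides for review of adverse events in real time and quarterly. That stands, and it confines the problem to the analysis set.

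Finally, section 14 announces a separate, detailed SAP. It could resolve the point, but no such text is in the documents.

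**Conclusion.** The wording of 14.1 is ambiguous. On one natural reading it removes first-period failures of the FEV1 check from the only defined safety set, mainly among NAC-first participants, and so favours NAC. At an assumed failure rate of 5–15% this is about 1 to 3 of about 18; the rate is not in the documents and the pilot is too small to narrow it.

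A reader might infer that everyone who bronchoconstricts on the first doses drops out, or that the safety result would omit NAC's main harm altogether. The documents do not support that. Falls that stay above the limit remain in the set, and reactions to NAC at Visit 8 in placebo-first participants remain too unless the second check is also read as eligibility. Nor do the documents show that exclusion was intended.

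This is a worthwhile, inexpensive correction rather than an essential one. Confidence is moderate, because it turns on which reading of one word is applied.

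**What to change.** - In 14.1 delete *eligible*, so that the Safety Population is all randomised participants who receive at least one dose of NAC or placebo.
- Assign each adverse event to the most recent treatment received. Decide before unblinding whether events that start in the washout are assigned to the period 1 treatment or shown separately.
- Tabulate failures of the FEV1 check by treatment and period.
- Describe the check consistently in the synopsis, 2.1, 6.2, 9.5 and 9.10 as one made after randomisation.
- Reconcile the differing statements of the check (at least versus greater than 80%, and which pre-treatment FEV1). Which threshold and baseline apply is for the investigators to settle; this review does not choose between them.

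The cost is one small extra table and a minor wording amendment, which needs IRB approval under 15.1. The definition of the set could also be confirmed in the SAP announced in section 14. The planned 36 participants, the visits and the data collected do not change.

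If the pre-randomisation reading was intended, deleting the word gives up nothing of value.

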### **4 STUDY DESIGN**

#### **4.1 Study Overview**

This is a multi-center, double-blind, randomized, 2 period crossover trial in 36 subjects with asthma who demonstrate mucus plugging on a screening CT lung scan. Screening data will be reviewed to determine participant eligibility. Participants who meet all inclusion criteria will self-administer nebulized 10% NAC (3 mL) and 2.5 mg albuterol inhalation solution (0.5 mL) or 0.9% saline (3 mL) and 2.5 mg albuterol inhalation solution (0.5 mL) to be taken 2 times per day for 14 days. Following an 8-week washout period, participants will be switched to the alternate group for 14 days of treatment. Participants will be assigned to the treatments in random order. Evaluations will be taken at baseline, end of first treatment, start of second treatment period, and at the end of the second treatment period.

The following treatment regimens will be used:

- Experimental treatment of 3.0 mL 10% NAC + 2.5mg/0.5 mL albuterol
- Placebo treatment of 0.9% saline + 2.5mg/0.5 mL albuterol

Total duration of participation will be 16 weeks. Total duration of the study is expected to be 2 years.

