## 7 STUDY TREATMENTS

### 7.1 Method of Assigning Participants to Treatment Groups

Up to 36 eligible patients will be randomly assigned to receive either the experimental treatment (10% NAC) or the placebo treatment (0.9% saline) during period 1 in a 1:1 ratio using a SAS-based computer-generated randomization scheme accessed by the investigational pharmacist. The UCSF investigational pharmacist will complete a randomization worksheet and log the group assignment for subjects enrolled at both UCSF and UC Davis. The UCSF investigational pharmacist will contact the UC Davis pharmacist by email or phone to inform them of the randomization. The randomization log will be shared with investigators upon study completion or in the event of a serious safety concern.

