### 7.4.2 Dispensing

Study medication will be dispensed by either, the study coordinator, study nurse or physician and only after observation of the administration of the first two doses of each treatment period.

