### **11.3 Replacement of Participants**

Participants who withdraw from the study treatment will be replaced.

Participants who withdraw from the study will be replaced.

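### Section 14.1 should drop the word 'eligible' from the Safety Population, because one inclusion criterion is tested only after randomisation and dosing

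*Combined protocol and SAP*

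**What the plan says.** - Section 14.1 is the only statement in section 14 about the safety analysis. It covers "All eligible participants who are randomized into the study and receive at least one dose of the study drug (the Safety Population". That sets three conditions: eligible, randomised, dosed.
- Section 6.2 (last item; synopsis item 10) lists as an inclusion criterion "Ability to tolerate study drug reflected by a post-treatment FEV1" of at least 80% of the pre-treatment, pre-bronchodilator value.
- Section 2.1 describes the same check as a condition for staying in: participants "will only be eligible to remain in the study if their post-treatment FEV1s are greater than 80% of their pre-treatment, pre-bronchodilator FEV1". It also states: "The main side effect from inhaled n-acetylcysteine (NAC) is bronchospasm".
- Section 9.5 fixes the order at Visit 4: randomisation is item 9, the two supervised doses with FEV1 before and after each are item 11, and the 80% check is item 12. Section 9.10 repeats the doses and the check at Visit 8. Under 7.4.2, take-home drug is released "only after observation of the administration of the first two doses of each treatment period".
- Section 11.3: "Participants who withdraw from the study will be replaced".
- Pointing the other way, 4.1 says "Screening data will be reviewed to determine participant eligibility", and 7.1 says "Up to 36 eligible patients will be randomly assigned".

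**The concern.** A participant who fails the check at Visit 4 has been randomised and has received study drug. The only word in 14.1 that can keep that person out of the Safety Population is *eligible*, and the protocol lists passing the check among its eligibility criteria. An analyst could follow the text and leave out the people who reacted to their first doses, and 11.3 would replace them. Bronchospasm is the harm the protocol expects from NAC, so any loss would fall on the outcome the safety analysis most needs to show. Membership of an analysis set should also not depend on which meaning of a word is chosen once the data are in.

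The same word has a second effect that does not depend on the tolerance check. Section 12 foresees participants who turn out not to have met the entry criteria. If they were dosed, 14.1 leaves them out under either reading.

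**Working it through.** **Step 1. Who is in the Safety Population under each reading of 14.1.**

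| Participant | Eligibility settled before randomisation | Eligibility includes the Visit 4 check |
|---|---|---|
| Fails the 80% check at Visit 4 | in | out |
| Passes at Visit 4, fails at Visit 8 | in | in |
| Dosed, later found to have missed another entry criterion | out | out |

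The second row is in under both readings because the criterion had already been met at Visit 4. Any loss of reactors is therefore confined to period 1. For NAC reactions, that means those randomised to NAC first. Someone who fails on saline in period 1 would be treated the same way.

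**Step 2. Illustrative size under the right-hand column.** The plan has no figure of its own to reproduce here. From the documents: 36 participants, allocated 1:1 (7.1), so about 18 take NAC first. Assumed: a proportion p fail the check on NAC, none fail on saline, and nobody leaves for another reason.

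With N randomised, true NAC failures are Np out of N. Half of them, Np/2, occur at Visit 4 and would be dropped from both numerator and denominator. The rate shown is (Np/2)/(N − Np/2) = p/(2 − p), whatever N is. The chance of losing at least one of 18 is 1 − (1 − p)^18.

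| Assumed p | Expected number dropped (18p) | Chance of at least one | Rate shown, p/(2 − p) |
|---|---|---|---|
| 2% | 0.36 | 30% | 1.0% |
| 5% | 0.9 | 60% | 2.6% |
| 10% | 1.8 | 85% | 5.3% |
| 20% | 3.6 | 98% | 11.1% |

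If a proportion q also fail on saline, the shown rate is p(1 − q)/[(1 − p) + (1 − q)]. At p = 10%, q = 2% gives 0.098/1.88 = 5.2%, and q = 5% gives 0.095/1.85 = 5.1%.

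**Step 3. The same with replacement.** If patients are replaced until 36 complete both periods, N = 36/(1 − p). At p = 10% that is 40 randomised, 4 failures on NAC and 2 of them at Visit 4. The full count is 4/40 = 10% (exact 95% CI 2.8% to 23.7%). After dropping it is 2/38 = 5.3% (0.6% to 17.7%). This assumes that replacement under 11.3 may take the number randomised above the 36 named in 7.1.

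**Step 4. What the documents offer on p.** Section 2.1 reports eight asthmatics given up to 3 mL of 20% NAC with albuterol, with a largest FEV1 fall of 6%. None would have failed an 80% check. Zero of eight has a one-sided 95% exact upper bound of 1 − 0.05^(1/8) = 31%. These data neither support nor exclude the rates in the table. The NAC was twice the trial's concentration and the albuterol volume also differed, so the comparison is loose.

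**Step 5. Under the left-hand column** no tolerance failure is dropped, so the effect in Steps 2 and 3 is zero. Only the third row of the first table is affected, and the documents give no basis for its size.

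**The case against.** The best counter-argument comes from 14.1 itself. If *eligible* meant having passed the check on the first two doses, every member would already be randomised and dosed, and the other two conditions would add nothing. They do some work only if eligibility comes before randomisation. Sections 4.1 and 7.1 use the word that way, and 2.1 speaks of being eligible to remain, which describes someone already in the study. This stands, and it makes the pre-randomisation reading the likelier one. It does not remove the conflict, because a criterion that needs study drug cannot be met from screening data. Nor does it help participants dosed and later found ineligible.

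A reader might infer that the trial will drop its NAC reactors and report about half the true rate of bronchospasm. The documents do not support that. It needs the less likely reading and a failure rate that appears nowhere in the text, and even at 10% the intervals 2/38 and 4/40 overlap heavily.

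A reader might also infer that acute FEV1 falls go unexamined. The supplied text plans no comparison by treatment of the supervised-dose readings. But 10.1 defines AEs broadly enough that a clinically relevant fall would ordinarily be recorded, 5.3 adds safety evaluations after 7 days in each period, and follow-up calls ask about side effects (9.6, 9.11). Only falls too small to be AEs would go uncompared.

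Finally, section 14 promises a detailed SAP that may settle both matters. It is not in the supplied text, and 14.1 is the rule as it now stands.

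**Conclusion.** The point holds as a wording fault in a stated analysis rule. Section 14.1 allows period 1 participants who bronchoconstrict on study drug to be left out of the safety analysis. Under the likelier reading it does not do so, but it still leaves out dosed participants later found ineligible. The size for tolerance failures is zero under the likelier reading. Under the other it is illustrative only: roughly half the NAC failures lost, given 1:1 sequences, an assumed failure rate, and few or no failures on saline. AE and SAE recording, ongoing review (8.1.17, 10.1, 10.2.1, 13), the tolerance rule and the primary analysis are untouched. The missing FEV1 comparison is a suggestion, not a defect.

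**What to change.** In 14.1, delete *eligible* and define the Safety Population as all randomised participants who receive at least one dose of study drug, including those who fail the 80% check and those later replaced, analysed by treatment received. All three rows of the first table are then in, whichever way eligibility is understood. The cost is one word deleted and one clause added, with no change to sample size, visits or the tolerance rule.

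Optional and secondary: add a descriptive table, by treatment received, of the FEV1 change around each supervised dose at Visits 4 and 8 and the number failing the 80% check. Both products contain albuterol, so the NAC-minus-saline contrast would show the acute effect of NAC itself. The readings are already scheduled; the cost is one table and a stated post-dose reading time.

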### **14.2 Demographic and Baseline Characteristics**

The following demographic variables at screening will be summarized: race, gender, age, height, weight, baseline FEV1, and baseline post-bronchodilator FEV1.

### 14.3 Analysis of Primary Endpoint

The primary analysis is a paired t-test analysis of the % change in FEV1 from the start to the end of the two-week treatment period with two times daily NAC (Mucomyst-10). The secondary analysis will be to determine how the change in FEV1 relates to the change in CT mucus score.

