CONTROL PRODUCT, DOSE AND ROUTE OF ADMINISTRATION	
0.9% saline (3mL) and 2.5 mg albuterol (0.5ml)
 
Product will be administered every 8-12hours (2 times per day) for 14 days. Medication will be administered via a portable nebulizer.

DURATION OF PARTICIPATION AND DURATION OF STUDY	
Participants will be enrolled in the study up to 178 days:
 
Screening: up to 90 days
 
Treatment Period 1: 14 days
 
Washout: 60 days
 
Treatment Period 2: 14 days
 
The total duration of the study is expected to be 24 months.
 
Participant recruitment will happen on a rolling basis.

CONCOMITANT MEDICATIONS	
Prohibited:
 
 
• thiols and thiol derivatives
 
• activated charcoal
 
• inhaled insulin
 

EFFICACY EVALUATIONS	
PRIMARY ENDPOINT	The primary outcome is the % change in FEV1 from the start to the end of the treatment period (either placebo or 10% NAC).
SECONDARY ENDPOINTS	
Secondary efficacy endpoints include:
 
 
• CT mucus score
 
• FVC
 
• PEF (AM and PM)
 
• Air trapping (RV/TLC ratio)
 
• FeNO
 
• Blood eosinophils
 

OTHER EVALUATIONS	Rheological properties of sputum.
SAFETY EVALUATIONS	Incidence of adverse events
PLANNED INTERIM ANALYSES	
No interim analysis is planned
 
Serious adverse events will be monitored by the ACRC data safety monitoring committee on an ongoing basis throughout the study.

STATISTICS Primary Analysis Plan	The primary outcome is the % change in FEV1 from the start to the end of the treatment period (either placebo or 10% NAC). The first analysis will be to test the assumption of negligible carryover effects from study period 1 to period 2. We will compare the sum of the outcome values measured in the two periods for each participant across the 2 sequence groups (placebo-10% vs. 10%-placebo) using an unpaired t-test. After no or negligible carryover effect has been confirmed, we will test for the difference in treatment effects between placebo and 10% NAC using a paired t-test.

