Rationale for Number of Participants	The primary goal of this study is to assess whether N-acetyl cysteine improves FEV1 after a 2-week treatment period in patients with asthma when compared to a two week treatment period of placebo. The study has a cross-over design which reduces the sample size. With help from [name]., biostatistician at Penn State, who has access to 2-week FEV1 data in NIH network trials and cohort studies in asthma that UCSF has participated in, we calculate a sample size of 36

	patients. This sample size is obtained when we factor in an effect size of 5% improvement in FEV1, a standard deviation for change in FEV1 of 20%, a within patient correlation for repeated measures of FEV1 of 0.9, and a power of 90%.
--	---

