### **5 CRITERIA FOR EVALUATION**

#### **5.1 Primary Efficacy Endpoint**

FEV1 will be the primary endpoint because it is the most robust measure of airflow obstruction in asthma. We will compare the post-treatment FEV1s to pre-treatment baseline values. We calculate that with a sample size of 36 we will have 90% power to detect an

effect size of 5% improvement in FEV1 and a within patient correlation for repeated measures of FEV1 of 0.9.

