### 14.6 Sample Size

We propose a sample size of 36, which will provide us with the power to examine the effect of NAC in a subgroup of individuals with asthma who have CT evidence of intraluminal mucus and to identify the CT mucus score that performs best as a biomarker of treatment response to NAC. Participants will be enrolled if their CT mucus scores are  $\geq 5.0$ . The sample size is obtained when we factor in an effect size of 5% improvement in FEV1, a standard deviation for change in FEV1 of 20%, a within patient correlation for repeated measures of FEV1 of 0.9, and a power of 90%.

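### The protocol contradicts itself on the primary analysis: the synopsis tests NAC against placebo, but section 14.3 describes only the change in FEV1 over the NAC period

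*Combined protocol and SAP*

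**What the plan says.** The design is stated without ambiguity in section 4.1: "This is a multi-center, double-blind, randomized, 2 period crossover trial in 36 subjects with asthma". Both regimens carry the same albuterol; the control is described there as "Placebo treatment of 0.9% saline + 2.5mg/0.5 mL albuterol".

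The accounts of the primary analysis differ by place:

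- **Synopsis, Primary Analysis Plan.** The outcome is defined for each treatment period: "The primary outcome is the % change in FEV1 from the start to the end of the treatment period (either placebo or 10% NAC". After a carryover check, "we will test for the difference in treatment effects between placebo and 10% NAC using a paired t-test".
- **Synopsis, Rationale for Number of Participants.** The goal is to see whether NAC improves FEV1 "when compared to a two week treatment period of placebo".
- **Section 14.3.** The primary analysis is a paired t-test of "the % change in FEV1 from the start to the end of the two-week treatment period with two times daily NAC". Placebo is not mentioned here or anywhere else in sections 14 to 14.6.
- **Section 5.1.** "We will compare the post-treatment FEV1s to pre-treatment baseline values". No treatment contrast is named.

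The opening of section 14 says that a detailed SAP will follow and will record any changes to the analyses set out in that section. Nothing states whether the synopsis or section 14 takes precedence.

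**The concern.** The synopsis asks whether NAC does better than placebo. Section 14.3, taken at its word, asks whether FEV1 moved during two weeks of NAC plus albuterol. These are different hypotheses, and only the first uses the randomised control.

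FEV1 could rise over a treatment period for reasons unrelated to NAC: the twice-daily nebulised albuterol, regression to the mean in people selected partly on low lung function, or time and repeated-visit effects. A before-after test credits all of these to NAC. The crossover contrast removes whatever is common to the two periods.

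Section 14.3 is the only statement of the primary test in the statistical section, so a SAP author who starts there could write the uncontrolled test in good faith. Two candidate primary tests also leave room for the choice to be made after the data are seen.

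**Working it through.** **Inputs.** From section 14.6 and the synopsis: "an effect size of 5% improvement in FEV1", an SD for change of 20%, a within-patient correlation of 0.9, power 90%, N = 36. Alpha is not stated; two-sided 0.05 is assumed. Changes are in percentage points of FEV1.

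**Step 1: reproduce N = 36 as NAC versus placebo.** Take 20 as the SD of one period's change and 0.9 as the correlation between the two periods' changes.

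- SD of the NAC-minus-placebo difference = 20 × √(2 × (1 − 0.9)) = 8.94.
- Normal approximation: ((1.960 + 1.282) × 8.94 / 5)² = 33.6, so 34.
- Exact noncentral t with n − 1 df: N = 36, power 90.3%. With n − 2 df, allowing for a fitted period effect, power is still 90.3%.
- A one-sided 0.05 test would give 29, which does not match.

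**Step 2: try N = 36 on the literal 14.3 test, keeping 20 as the SD of change.** One-sample test of the NAC-period change: ((1.960 + 1.282) × 20 / 5)² = 168.1, exact N = 171. Power at 36 is 30.8%. This does not match.

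**Step 3: try the other reading of the inputs.** If 20% is the SD of a single FEV1 and 0.9 is the pre-post correlation, the SD of one period's change is again 20 × √0.2 = 8.94, and a NAC-only before-after test also gives N = 36. The sample size therefore favours the placebo contrast on the stated wording but does not settle the matter. On this second reading the difference between the two periods' changes has SD 8.94 × √(2 × (1 − r)), where r is their correlation (assumed range):

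| r | SD of difference | N for 90% power | Power at 36 |
|---|---|---|---|
| 0 | 12.65 | 70 | 64% |
| 0.25 | 10.95 | 53 | 76% |
| 0.5 | 8.94 | 36 | 90% |

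**Step 4: size of the bias if 14.3 is followed literally.** Suppose NAC is inert and FEV1 rises by c points in both periods for other reasons. The values of c are illustrative; the documents give no estimate. The NAC-only test on 36 participants has 35 df and noncentrality c × √36 / SD = 6c / SD. The probability of a significantly positive result is:

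| c | SD 20 (as stated): 6c/SD | Probability | SD 8.94 (second reading): 6c/SD | Probability |
|---|---|---|---|---|
| 2 | 0.60 | 8% | 1.34 | 26% |
| 3 | 0.90 | 14% | 2.01 | 50% |
| 5 | 1.50 | 31% | 3.36 | 90% |

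With no such rise the figure would be 5% / 2 = 2.5%. For NAC minus placebo the expected difference is c − c = 0, so the test keeps its 5% two-sided level whatever the value of c.

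**The case against.** The strongest reply is that section 14.3 is shorthand. A % change is already one number per period, so a paired test of it needs a second % change to pair with, and in this design that is the placebo-period change, as the synopsis says. Section 5.1 can likewise be read as defining a change score to be computed in each period; it names no test and does not single out NAC. On the stated SD for change, N = 36 fits the placebo contrast and not a NAC-only test.

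Much of this stands. It makes the synopsis the more likely intention, but it does not remove the conflict: a loosely worded end-versus-start test within the NAC period is also a natural reading of 14.3, and a primary analysis should not have to be inferred.

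The albuterol route also has limits. Section 8.1.2 gives a 4-hour hold for short-acting beta-agonists before visits with reversibility testing. That hold is worded as a request that may be made, and a clinician may shorten or waive it. Regression to the mean and time or visit effects are untouched by it.

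A reader might infer more than the documents support:

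- **That the randomised comparison has been lost.** It has not. It remains in the synopsis as the Primary Analysis Plan, and both periods are measured.
- **That section 14 overrides the synopsis.** Section 14 is the text that the SAP is expected to modify, but no sentence ranks it first.
- **That 26%, 50% and 90% follow from the plan's inputs as worded.** They need the 20% to be the SD of a single FEV1. The stated SD for change gives 8%, 14% and 31%.

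**Conclusion.** The contradiction is real and bears on what the primary p-value means. As written, section 14.3 omits the placebo contrast that the synopsis specifies; followed literally, it yields an uncontrolled before-after test. The harm arises only if an analyst takes that reading over the synopsis, so this is an unreconciled primary analysis and not a plan that has settled on an uncontrolled one.

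The size under the literal reading depends on a rise unrelated to NAC that nobody has estimated, on the assumed alpha, and on which SD the 20% describes. It shows how quickly false claims could accumulate; it does not predict this trial's error rate. That power is unchanged by the correction holds on the stated wording of the inputs. It would not hold on the second reading unless the two periods' changes correlate at about 0.5 or more.

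**What to change.** Reword section 14.3 so that the single primary analysis is the within-participant comparison of % change in FEV1 between the NAC and placebo periods, as the synopsis already has it. Align section 5.1 by saying that the change is computed in each period and then compared between treatments. Report the change within the NAC period descriptively only. The paired t-test is enough to resolve the contradiction; a period term is optional and on the stated inputs leaves power at 90.3%.

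In the same edit, state alpha and sidedness, and say which quantities the 20% and the 0.9 describe, since the power of the placebo comparison turns on this.

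The cost is a few sentences in the protocol, carried into the SAP before the data are analysed. No new data are needed. No extra participants are needed if 20% is the SD of change and 0.9 correlates the two periods' changes.
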